4.4 Blinding

4.4.1 Blinding Method

Study drug administration is implemented in a double-blind, placebo-controlled manner. Neither the subjects nor the investigators and their staff can distinguish the roxadustat tablets from the matching placebo tablets. Both will be identical in appearance, packaging and labeling in order to maintain the blind.

Randomization of treatments and preservation of the treatment blind are maintained by an Interactive Response Technology (IRT). The randomization code will remain confidential until completion of the study.

4.4.2 Retention of the Assignment Schedule and Procedures for Treatment Code Breaking

The randomization schedule will be generated under the responsibility of the Global Data Science (GDS) Department, Astellas Pharma Europe B.V. (see Section 4.5). The vendor of the IRT used in this study will receive the randomization schedule and perform the random assignments of medication numbers to study treatments. These files will be held securely and will be released to the study biostatistician only after database hard lock has taken place and a decision has been taken to unblind the study.

Procedures for emergency unblinding of individual subjects, in the event that knowledge of the treatment assigned is required for the correct management of a medical emergency, are described in [Section 4.4.3]. Emergency unblinding of a few individual subjects does not, in general, affect the continued blinding of other subjects in the study or the scientific integrity of the study.

The Independent DSMB see [Section 10.1], will have access to group-unblinded and/or fully unblinded DSMB reports. They will also be authorized to access the unblinded treatment for single subjects or for single treatment groups via the IRT. The DSMB will not disclose this information to any other staff involved in this study.

4.4.3 Breaking the Treatment Code for Emergency

For each randomized subject, individual code breaks will be accessible in the event of a medical emergency requiring knowledge of the treatment assigned to the subject. The code is accessible through the IRT. The time and date of any code break will automatically be documented in the IRT.

Only the responsible investigator or delegates duly registered in the study file as sub-investigators can break the code via the IRT. Subjects or other study personnel will not be made aware of the treatment given to any subject unless a medical emergency necessitates such disclosure. Any breaking of the treatment code by the investigational staff must be reported immediately to the 24-hour contact for SAEs [see Section II] and must include an explanation for breaking the code. The sponsor should be contacted to discuss the case, if possible, prior to unblinding. The date of breaking the blind, person who requested the blind

to be broken, person who broke the blind, the reason for breaking the blind, and the person informed at the sponsor will be captured in the eCRF.

Unplanned unblinding may result in the discontinuation of subject participation from the study.

4.4.4 Breaking the Treatment Code by the Sponsor

The sponsor's personnel from the Drug Safety and Pharmacovigilance Department may break the treatment code for subjects who experience a Suspected Unexpected Serious Adverse Reaction (SUSAR), in order to determine if the individual case or a group of cases requires expedited regulatory reporting. Individual Emergency Code will be provided to the limited staff who are empowered to break the codes for all SUSAR cases for reporting purposes.

4.5 Assignment and Allocation

Assignment to treatment groups will be done using the randomization scheme prospectively prepared by [REDACTED] on behalf of the sponsor, under the responsibility of the GDS Department of APEB. Automated randomization and treatment assignments will be provided by an IRT.

A total of 450-600 planned subjects will be randomized to receive 1 of the 2 treatment arms in a 2:1 ratio as follows:

- Roxadustat (planned 300-400 subjects)
- Placebo (planned 150-200 subjects)

Randomization will be stratified by the following 4 factors:

- Region (region A versus region B)*
* assignment to region will be determined based on health care system comparability
- Screening Hb values (≤ 8.0 g/dL versus > 8.0 g/dL)
- History of cardiovascular, cerebrovascular or thromboembolic diseases (Yes versus No)
- eGFR (< 30 mL/min/1.73 m² versus ≥ 30 mL/min/1.73 m²)

5 TREATMENTS AND EVALUATION

Subjects must provide a signed Informed Consent Form (ICF) and be registered in IRT before any screening tests or assessments are performed. Participating study sites are required to document all screened candidates who provided Informed Consent. If a subject is later excluded from the study, the reasons for exclusion will be documented in the subject's source documents in the eCRF.

Registration of subjects into the study, assignment of subject identification numbers, and randomization will take place using a centralized IRT technology. After obtaining consent, and prior to the start of screening assessments, the investigator will register the subject in IRT, which starts the 42 day Screening Period, and a subject identification number will be assigned. No screening tests or assessments should be performed prior to registration and

assignment of a unique subject identification number by IRT. Any subject identification numbers that are assigned will not be reused even if the subject does not receive treatment.

If a subject's laboratory parameter results do not meet the inclusion criteria or meet the exclusion criteria at Screening, the laboratory parameter assessment may be repeated once within the 42-day screening period. This includes an additional (4th) Hb value that may be collected if necessary. The mean of 3 most recent Hb values during the 42-day screening period, obtained at least 4 days apart, will be used to assess the subject's eligibility.

If a subject fails screening, they will be registered in IRT as a screen failure and considered out of the study. However, the subject may be re-screened once (immediately or later) if deemed appropriate by the investigator. When a subject will be re-screened, the subject must be re-consented, a new 42-day screening period starts and all screening procedures must be repeated. Subject must also be registered in IRT as re-screened under the same subject number as first screening.

Subjects confirmed not eligible after screening or, if applicable, after re-screening, should be registered in IRT as a screen/re-screen failure.

5.1 Dosing and Administration of Study Drugs and Other Medications

5.1.1 Dose/Dose Regimen and Administration Period

Following the screening period, eligible subjects will enter the treatment period upon randomization. Subjects will be randomized via IRT to receive roxadustat or placebo. The initial study drug dose is based on the tiered, weight-based dosing scheme [refer to [Table 2](#)]. The first study drug administration should be on the day of randomization, i.e., day 1, after all study assessments have been completed.

Scheduled Visits

During the Treatment period, subjects will attend weekly study visits from day 1 to week 2, followed by every other week study visits from weeks 4 to 24 and thereafter every 4 weeks until the EOT.

Study drug will be dispensed to subjects at each study visit during the treatment period with instructions for self-administration of the tablets on each dosing day, according to the dosing schedule. The study drug tablets are to be swallowed whole with room-temperature drinking water.

All subjects will administer study drug TIW and study drug doses must be administered at least 2 days apart, and no more than 4 days apart. Investigators and subjects should make every effort to keep dosing days and dosing times consistent throughout the study.

Dosing Instructions for Subjects Moving from Protocol v1.0 to Protocol v2.0

Subjects who entered the study under protocol v1.0 should, upon signing the updated informed consent, adapted their dose frequency and dose amount according to the instructions in [Appendix 3](#) Instructions for Subjects Moving from Protocol v1.0 to Protocol v2.0.

There were no adaptations to dose frequency or dose amount for subjects moving from Protocol v2.0 to Protocol v2.1.

5.1.2 Changes in Study Drug Dose

Dose adjustments are permitted from week 4 onward, and every 4 weeks thereafter. All dose adjustments are made to maintain study subjects' Hb level within the predefined target range and are based on Hb values using the HemoCue® device, a point-of-care device.

Dose adjustments will follow unique dose adjustment rules [Table 3](#).

Table 3 Dose Adjustment Rules

Change in Hb over past 4 weeks (g/dL) ^a	Correction Period	Maintenance Period		
	(When Hb correction has not been reached)	Hb <10.5 g/dL	Hb 10.5 to <12.0 g/dL	Hb 12.0 to <13.0 g/dL
< -1.0	↑	↑	↑	No change
-1.0 to 1.0	↑	↑	No change	↓
> 1.0	No change	No change	↓	↓

^a Subtract 4 weeks' previous Hb value from the present Hb value to calculate the change.

- All dose adjustments are made based on Hb values using HemoCue, a point-of-care device.
- If the dose adjustment is 'No change' per [Table 3](#), the next dose adjustment review is 4 weeks after that visit.
- Dose increases by 1 dose step (↑) and reductions by 1 dose step (↓) are pre-set per the dose steps.
- The dose steps are as follows: 20, 40, 50, 70, 100, 150, 200, 250 and 300 mg.
- The maximum dose is the dose step corresponding to 3.0 mg/kg per administration or 300 mg, whichever is lower. The default weight is initially set as weight measured at day 1. At study visits where weight is collected, the maximum allowed dose step and the default weight for a subject will be adjusted if the weight change is ≥ 5% compared to the previous default weight collected in the study. For randomized subjects who require chronic dialysis during the treatment period, the maximum dose step is the dose step corresponding to 3.0 mg/kg per administration or 400 mg, whichever is lower.
- At week 4 only, in a subject whose BL Hb level was < 8.0 g/dL, if the dose adjustment is to increase, then dose increase could be made with either a 1 or 2 step increase per investigator's discretion to minimize the probability of requiring rescue therapy treatment.

- Contact the Medical Monitor if dose adjustments would lead to doses outside the limits of the dose step range; i.e., lower than 20 mg or higher than 300 mg.
- If there is a safety concern, investigators may deviate from the dose adjustment rules. This should be discussed with the Medical Monitor and documented in the source documentation.

At Any Time when Hb \geq 13.0 g/dL

- Stop dosing
- Resume dosing when Hb < 12.0 g/dL at a dose that is reduced by 2 steps
- Next dose adjustment review is 4 weeks after dose resumption and in 4-weekly intervals thereafter.

Dose Adjustment for Excessive Hematopoiesis

At any time during the Treatment Period:

- If Hb increases by > 2.0 g/dL within 4 weeks, the dose should be reduced by 1 dose step.

Note: Only 1 dose reduction for excessive hematopoiesis is recommended within a period of 4 weeks. If a blood transfusion or ESA rescue treatment has been performed within 2 weeks of meeting the criteria for excessive hematopoiesis, it is recommended not to perform a dose reduction for excessive hematopoiesis.

After a dose adjustment due to excessive hematopoiesis, the subject's next dose adjustment review will occur 4 weeks later, and in 4-weekly intervals thereafter. If the dose adjustment interval falls on a non-visit study week, the dose adjustment review should be performed at the next scheduled clinic visit.

5.1.3 Previous and Concomitant Medication (Drugs and Therapies)

5.1.3.1 Previous Medication (Drugs and Therapies)

Previous medications are any prescription or over-the-counter preparations, including herbal products and "natural remedies", used by a subject prior to Screening.

If not specified differently, intake of any previous medication within 4 months prior to randomization should be documented in the eCRF. The medication name, start and stop date, route, dose, frequency and indication for each medication will be entered in the eCRF.

The last treatment course of any previous treatment type received for anemia (medication or procedures such as ESAs, iron (IV or oral), and RBC transfusions) within 12 months prior to randomization will be documented in the eCRF. The medication name, start and stop date, route, dose, frequency and indication for each medication will be entered in the eCRF.

The following previous medication is not permitted:

- Any ESA within 12 weeks prior to randomization
- IV iron (more than 1 dose) within 12 weeks prior to randomization
- RBC transfusion within 8 weeks prior to randomization
- Iron-chelating drugs within 4 weeks prior to randomization

- Any investigational drug within 30 days or 5 half-lives or limit set by national law (whichever is longer), prior to the initiation of Screening
- Roxadustat or another HIF-PHI at any time.

5.1.3.2 Concomitant Medication (Drugs and Therapies)

Concomitant medications are any prescription or over-the-counter preparations, including herbal products and “natural remedies”, used by a subject from informed consent to EOS visit. The medication/therapy name, start and stop date, route (if applicable), dose and frequency and indication for each medication/therapy will be entered in the eCRF.

For all concomitant medication use, from screening visit to EOS visit, the study site must provide an indication for its use. If the stated indication is a non-specific condition, e.g., “rash”, documentation of the condition, as specific as possible, should be maintained in the subject’s clinical study records as source documentation.

Statins and Other Substrates for OATP 1B1

There is a risk that roxadustat will increase the plasma levels of statins and other drugs that are substrates of OATP 1B1, based on results from drug-drug interaction studies. Because statin dose has been known to be associated with the risk for side effects such as myopathy, (e.g., myalgia, myositis and rhabdomyolysis), the investigator is advised to consider this potential interaction between roxadustat and statins when deciding on the appropriate dose of statins based on efficacy and safety of statin therapy. Switching to a non-interacting statin (e.g., pravastatin) may be considered. Furthermore, it is recommended not to exceed the proposed maximum daily dose of statins as outlined in [Table 4](#).

The investigator is also advised to consider this potential interaction between roxadustat and other drugs that are substrates for OATP 1B1 when deciding on the appropriate posology of these drugs. Examples of these drugs are atrasentan, bosentan, ezetimibe, repaglinide, glyburide, SN-38 (active metabolite of irinotecan), rifampin, valsartan and olmesartan. It is recommended to refer to the Summary of Product Characteristics (SmPC) of these drugs for further details and guidance.

Table 4 Proposed Maximum Daily Dose of Statins Not to Be Exceeded

Statin	Proposed maximum dose (mg/day)
Simvastatin	20 GFR < 30 mL/min: 5
Atorvastatin	40
Rosuvastatin	10 Severe renal impairment: no recommendation as contraindicated in this case
Fluvastatin	40 GFR < 30 mL/min: 20
Pravastatin	40
Pitavastatin	2 GFR < 30 mL/min: 1

Phosphate Binders and Other Multivalent Cation-containing Drugs and Mineral Supplements

Results from a drug-drug interaction study demonstrated a significant reduction in roxadustat plasma exposure when a single dose of roxadustat was administered simultaneously with the phosphate binders sevelamer carbonate or calcium acetate.

Subjects should take roxadustat in a consistent manner relative to their phosphate binder intakes, and discuss with the investigator before changing their phosphate binder dose or dosing time. To reduce the effect of phosphate binders on roxadustat exposure, subjects should be advised that roxadustat be taken at least 1 hour before or 1 hour after their phosphate binder.

It is anticipated that other multivalent cation-containing drugs and mineral supplements (e.g., iron, calcium, magnesium, aluminum), sucralfate or magnesium- or aluminum-containing antacids would produce a similar interaction; therefore, administration of roxadustat between -1 hour and +1 hour of intake of these preparations is not recommended.

Anti-hypertensive Medications

To avoid confounding effects on study endpoints, changes to anti-hypertensive medications should be kept to a minimum during the course of the study, and only if deemed medically necessary by the investigator. Changes to anti-hypertensive medications will be documented in the eCRF.

Supplemental Vitamin B12, Folate

Vitamin B12 and folate can be taken without restriction at any time during the study.

Supplemental Iron and ESA Use

Oral iron is recommended as the first-line treatment for iron supplementation and can be taken without any restriction. However, IV iron and ESA use is restricted to use as rescue therapy, see rescue therapy guidelines, [Section 5.1.5]. Administration of roxadustat between -1 hour and +1 hour of intake of oral iron is not recommended.

Prohibited Medications

The following medications are prohibited during the period identified:

- Iron-chelating agents (e.g., deferoxamine, deferiprone, or deferasirox therapy) from 4 weeks prior to randomization until EOS visit
- Androgens from randomization until EOS visit
- Dapsone in any dose amount or chronic use of acetaminophen (paracetamol) > 2.0 g/day from randomization until EOS visit
- Any hypoxia-inducible factor HIF-PHI other than roxadustat, as allocated by randomization, until EOS visit.

Use of herbal medicine is not prohibited but strongly discouraged during the course of the study.

5.1.4 Treatment Compliance

The quantity of study drug dispensed to and returned by the subject will be counted and recorded in the eCRF [see Section 5.1.1]. If the subject is not compliant with study drug intake, the investigator should discuss this with the subject. Deviations from the prescribed dose should be entered into the eCRF and require notification to the Sponsor (see Sections 7.8 and 8.1.6).

5.1.5 Rescue Therapy Guidelines

Rescue therapy guidelines are provided to optimize standardization of the use of rescue therapy by investigators and to ensure safety of the individual study subjects. Use of rescue therapy and reason for rescue therapy should be recorded in the eCRF. If subjects meet the criteria for ESA rescue therapy whilst on dialysis, ESAs will be administered IV or SC according to the Package Insert or SmPC of the respective ESA for dialysis patients.

RBC Transfusion

In the event of acute or severe blood loss, RBC transfusion is allowed if clinically indicated. In a situation where there is no obvious blood loss, RBC transfusion will be permitted if the subject has moderate to severe symptom(s) from his/her anemia, e.g., dyspnea at rest or on mild exertion, and the investigator is of the opinion that the blood transfusion is a medical necessity. Study drug may be continued even if a blood transfusion had been administered.

ESA

If a subject's Hb level has not sufficiently responded to 2 or more dose increases or maximum dose (by body weight) of the study drug and the investigator considers the initiation of an ESA (i.e., EPO analogue) rescue as a medical necessity, the investigator should consider initiating the use of an approved ESA only if all of the following criteria are met:

- The subject's Hb level has not sufficiently responded to 2 or more dose increases in previous 8 weeks or maximum dose (by body weight) of the study drug; **and**
- The subject's Hb is < 8.0 g/dL; **and**
- Reducing the risk of alloimmunization in transplant eligible subjects and/or reduction of other RBC transfusion-related risks is a goal.

The subject may continue on study, however, the subject is not allowed to be administered both ESA and study drug during the same time period. The course of ESA (i.e., the amount that may be administered) will be limited by duration of therapy and effect on Hb, including that 1 course of ESA treatment will not exceed 4 weeks in duration, and that ESA rescue will be stopped as soon as Hb \geq 9 g/dL. Treatment with study drug may be resumed as soon as possible after the following intervals:

- At least 2 days after stop of Epoetin alfa or Epoetin beta, or biosimilar thereof
- At least 1 week after stop of darbepoetin alfa
- At least 2 weeks after stop of methoxy polyethylene glycol-epoetin beta.

If a subject requires a third course of rescue with ESAs, the subject must be discontinued. The subject will complete the EOT visits (EOT visit and EOT + 2 weeks visit) and the EOS visit, and will continue to be followed up on 6-monthly frequency for vital status and SAEs, cardiovascular and thromboembolic AEs until their projected date of completion or, if earlier, until the last subject randomized reaches EOS.

For instructions on ESA rescue treatments for subjects moving from protocol v1.0 to protocol v2.0, see [Appendix 3](#)

Intravenous Iron

Oral iron is recommended for dietary supplementation to support erythropoiesis and as the first-line for prevention and treatment of iron deficiency, unless the subject is intolerant to this route of treatment. The recommended daily oral dose is 200 mg of elemental iron.

The investigator may initiate the use of IV iron supplement if:

- The subject's Hb level has not sufficiently responded to 2 or more dose increases of study drug while taking oral iron (unless not tolerated), and
- Hb < 8.5 g/dL, and
- Ferritin < 100 ng/mL, or TSAT < 20%.

If IV iron rescue criteria are met, the dose in a single administration (day) should be no more than 250 mg. Study treatment may continue during IV iron administration. At 4 to 8 weeks after the single dose of IV iron, a repeat dose of IV iron can be administered if the Hb remains < 9.0 g/dL and the subject still meets iron deficiency criteria (ferritin < 100 ng/mL or TSAT < 20%). After this 8-week period, full IV iron rescue criteria would need to be met again in order to qualify a subject for a second course of IV iron at a later point in the trial.

In Case of Excessive Hematopoiesis

If a blood transfusion or ESA has been performed within 2 weeks of meeting the criteria for Excessive Hematopoiesis, it is recommended not to perform a dose reduction of the study drug for excessive hematopoiesis.

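### Subjects of 45.0–49.9 kg normally cannot meet the IV iron rescue criterion, because only one dose increase is open to them and, unlike the ESA criterion, it has no maximum-dose alternative

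*Protocol*

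**What the plan says.** Protocol 5.1.5 introduces its criteria as guidance: "Rescue therapy guidelines are provided to optimize standardization of the use of rescue therapy by investigators". The three rescue routes are set out as follows.

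- **IV iron.** "The investigator may initiate the use of IV iron supplement if" the subject's Hb "has not sufficiently responded to 2 or more dose increases of study drug while taking oral iron" (oral iron being waived if not tolerated), Hb is below 8.5 g/dL, and ferritin is below 100 ng/mL or TSAT below 20%. "Study treatment may continue during IV iron administration".
- **ESA.** The response criterion is failure on "2 or more dose increases in previous 8 weeks or maximum dose (by body weight) of the study drug". Hb must also be below 8.0 g/dL, and reducing transfusion-related risk must be a goal. During a course, "the subject is not allowed to be administered both ESA and study drug during the same time period".
- **Transfusion.** It is allowed for acute or severe blood loss. Otherwise "RBC transfusion will be permitted if the subject has moderate to severe symptom(s) from his/her anemia" and the investigator judges it a medical necessity.

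Section 5.1.3.2 adds that "IV iron and ESA use is restricted to use as rescue therapy". Dosing is governed by Sections 2.2.2 and 5.1.2: a 70 mg start up to 70 kg and 100 mg above, a fixed list of dose steps, and a maximum of 3.0 mg/kg or 300 mg, whichever is lower. Inclusion criterion 10 admits subjects from 45.0 kg.

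**The concern.** The IV iron criterion counts dose increases, but the number available depends on body weight. If the weight cap stops titration after one increase, the count of two cannot be reached, however poor the response. The ESA criterion, in the same section, deals with this by accepting the maximum dose by body weight. The IV iron criterion does not, and no reason for the difference is given.

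What is at stake is access to a listed rescue treatment for a small group of eligible subjects. Because IV iron is reserved for rescue, failing the criterion leaves no other listed way to receive it.

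**Working it through.** The documents give no figure for this point, so there is none to reproduce. The check is a count along the dose ladder.

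**Inputs**
- Eligible weight: 45.0–160.0 kg (3.1, criterion 10).
- Start: 70 mg up to 70 kg, 100 mg above (2.2.1.3.2, 2.2.2).
- Steps: 20, 40, 50, 70, 100, 150, 200, 250, 300 mg (5.1.2).
- Ceiling: 3.0 mg/kg or 300 mg, whichever is lower (2.2.2, 5.1.2). Appendix 3 says the assigned dose must not exceed it, so the top step is found by rounding down.
- Reviews from week 4, then every 4 weeks, normally one step each (5.1.2).

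**Formula.** Top step = highest listed step ≤ min(3.0 × weight, 300). Increases available = number of steps from the starting dose to the top step. Evaluated in 0.1 kg increments:

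| Weight (kg) | Start (mg) | 3.0 mg/kg (mg) | Top step (mg) | Increases available |
|---|---|---|---|---|
| 45.0–49.9 | 70 | 135.0–149.7 | 100 | **1** |
| 50.0–66.6 | 70 | 150.0–199.8 | 150 | 2 |
| 66.7–70.0 | 70 | 200.1–210.0 | 200 | 3 |
| 70.1–83.3 | 100 | 210.3–249.9 | 200 | 2 |
| 83.4–99.9 | 100 | 250.2–299.7 | 250 | 3 |
| 100.0–160.0 | 100 | 300 or more, capped at 300 | 300 | 4 |

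The affected band is 45.0–49.9 kg. Its maximum is reached at week 4. From 50.0 kg the second increase is possible from week 8. The 400 mg limit for dialysis subjects changes nothing here, because 3.0 mg/kg is the binding limit.

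**Ways round the count**
- *Week-4 two-step increase (baseline Hb < 8.0 g/dL).* Two steps from 70 mg is 150 mg, above the cap in this band.
- *Weight gain.* The cap is reset only on a change of at least 5%, and 150 mg needs 50.0 kg. Weight needed = max(50.0, 1.05 × day-1 weight). From 45.0 kg: 50.0 kg (+5.0 kg, 11.1%). From 47.6 kg: 50.0 kg (+2.4 kg, 5.0%). From 49.9 kg: 52.4 kg (+2.5 kg, 5.0%). The first scheduled weight after day 1 is at week 12, 4 weeks after a 50 kg subject could have had the second increase.
- *Down, then up.* A subject reduced to 50 mg and later raised to 70 and 100 mg has had two increases.
- *Protocol v1.0.* The Appendix 3 conversion table lists a 120 mg step, so 70 to 100 to 120 mg was possible.

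**Consequence in the band.** Take an iron-deficient subject at 100 mg with Hb 8.0 to <8.5 g/dL, no blood loss and no moderate-to-severe symptoms. IV iron fails on the count of increases, ESA fails because Hb is not below 8.0 g/dL, and transfusion fails for want of blood loss or symptoms. A subject of 50 kg or more can be in the same position, but only until a second increase has been tried. Below 50 kg it normally does not end. If Hb falls below 8.0 g/dL, ESA opens through the maximum-dose route, provided its transfusion-risk criterion is met, but study drug must be interrupted. IV iron, which can be given alongside study drug, stays unlisted.

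**The case against.** The arithmetic is not in dispute. The case on the other side is about how much it matters.

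- *It is guidance.* The wording is permissive, IV iron is not on the prohibited list in Appendix 1, and oral iron, transfusion for symptoms and physician-decision discontinuation remain open. This stands as mitigation. It leaves a case-by-case workaround to text meant to standardize rescue. The safety exception in 5.1.2 covers the dose adjustment rules, not the rescue criteria, and rescue judged to deviate significantly can exclude a subject from the per-protocol set (SAP 5.3, criterion 8).
- *Down-then-up titration is not rare.* Section 2.2.2 expects a weekly dose 22% to 35% lower in maintenance. One step down from 70 to 50 mg is 20/70 = 29%, and the IV iron criterion has no time window. This stands for roxadustat responders who later lose response. It does not help the likeliest candidates, placebo subjects and initial non-responders, who would not normally have been titrated down.
- *Iron-replete subjects at Hb 8.0 to <8.5 g/dL also lack a listed rescue, at any weight.* True, but IV iron is not indicated for them. Here the indication is present and only the count fails.
- *The ESA and IV iron criteria differ in several other ways, so they need not match.* They need not. But nothing in the documents explains a requirement that an eligible weight band normally cannot meet.
- *The numbers are tiny and the timing late.* This stands. The SAP revision history (version 3.0, item 15) describes very few subjects with IV iron. The synopsis plans completion in 4Q2017, so the practical gain depends on a further amendment being made while subjects are still on treatment.

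**Conclusion.** The point holds as a minor patient-safety and consistency defect. At 45.0–49.9 kg the IV iron criterion is normally unreachable; at every weight from 50.0 kg it can be reached. The Hb range with no listed rescue for an iron-deficient subject in this band, absent blood loss or qualifying symptoms, is 8.0 to <8.5 g/dL.

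The conclusion assumes current dose steps, stable weight, no earlier dose reduction, no increases carried over from v1.0, and 3.0 mg/kg as a ceiling. Reading the maximum as the nearest step would give 150 mg at 45.0 kg, but 150/45.0 = 3.33 mg/kg, which breaches the ceiling. The documents give no weight distribution, so no count of affected subjects can be stated; it is probably very few. No bias between arms and no effect on any endpoint is claimed.

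**What to change.** In the first IV iron criterion of Protocol 5.1.5, insert *or maximum dose (by body weight)* after the requirement for two or more dose increases, keeping the oral iron condition as it is. This matches the ESA criterion.

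At constant weight and with one-step increases, the change affects eligibility only at 45.0–49.9 kg, because every heavier subject reaches the maximum only after two or more increases. It would also settle a side question: at 50.0–66.6 kg (70 to 150 mg) and 70.1–83.3 kg (100 to 200 mg) a two-step increase at week 4 reaches the maximum in one adjustment, and the protocol does not say whether that counts as one increase or two.

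The cost is one phrase, with no new data and no change to dosing or analysis. Because it touches subject safety, Section 8.3.3 requires IRB/IEC approval before it takes effect, across about 200 centres. It should therefore go into the next protocol amendment and does not justify one of its own.
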